NON-INTERVENTIONAL (NI) STUDY PROTOCOL

Study Information

Title	Investigating uptake and subsequent health outcomes associated with Pfizer-BioNTech bivalent COVID-19/Influenza vaccine concomitant administration using a claims-based real-world data source in the US
Protocol number	C4591061
Protocol version identifier	1.0
Date	26 April 2023
Active substance	J07BN01
Medicinal product	Pfizer-BioNTech BA.4/5 bivalent mRNA COVID-19 vaccine
Research question and objectives	
The primary objectives are:
 
• To describe the proportion of Pfizer-BioNTech bivalent mRNA COVID-19/influenza vaccines that are concomitantly administered, and the characteristics of patients who receive concomitant administration.• To estimate vaccine effectiveness (VE) of concomitant administration of a single dose of the mRNA Pfizer-BioNTech bivalent COVID-19 vaccine and a licensed flu vaccine versus either vaccine alone against all-cause hospitalization or acute respiratory illness requiring hospitalization, emergency department/urgent care or outpatient encounters.
[name], MHS Pfizer Inc. PPD

PFIZER CONFIDENTIAL

Co-Author	PPD PPD [REDACTED], MS, MBA Pfizer Inc. PPD [REDACTED] [REDACTED]
------------------	--

This document contains confidential information belonging to Pfizer. Except as otherwise agreed to in writing, by accepting or reviewing this document, you agree to hold this information in confidence and not copy or disclose it to others (except where required by applicable law) or use it for unauthorized purposes. In the event of any actual or suspected breach of this obligation, Pfizer must be promptly notified.

PFIZER CONFIDENTIAL

2. LIST OF ABBREVIATIONS

Abbreviation	Definition
AE	Adverse Event
AIDS	Acquired Immunodeficiency Syndrome
CI	Confidence interval
CDC	Centers for Disease Control and Prevention
CFR.	Code of Federal Regulations
CIOMS	Council for International Organizations of Medical Sciences
CKD	Chronic Kidney Disease
CDM	Clininformatics Data Mart
COVID-19	Coronavirus Disease 2019
CPT	Current Procedural Terminology
ED	Emergency Department
EMA	European Medicines Agency
ENCePP	European Network of Centres for Pharmacoepidemiology and Pharmacovigilance
FDA	Food and Drug Administration
GPP	Guidelines for Good Pharmacoepidemiologic Practice
HCPCS	Healthcare Common Procedure Coding System
HIPAA	Health Insurance Portability and Accountability Act
HIV	Human Immunodeficiency Virus
HR	Hazard ratio
ICD-10-CM	International Classification of Diseases, 10 th revision,

PFIZER CONFIDENTIAL

Abbreviation	Definition
	Clinical Modification
IEC	Independent Ethics Committee
IPTW	Inverse Probability of Treatment Weights
IRB	Institutional Review Board
ISPOR	International Society for Pharmacoeconomics and Outcomes Research
ISPOR-ISPE	International Society for Pharmacoeconomics and Outcomes Research – International Society for Pharmacoepidemiology
mRNA	Messenger Ribonucleic Acid
NDC	National Drug Code
NVX-CoV2373	Novavax COVID-19 vaccine
NY	New York
POS	Place of service
SARS-CoV-2	Severe Acute Respiratory Syndrome Coronavirus 2
SAS	Statistical Analysis System
SCD	Sickle cell disease
SD	Standard Deviation
SIV	Seasonal Influenza Vaccine
UC	Urgent care
UK	United Kingdom
US	United States
VAERS	Vaccine adverse event reporting system

Abbreviation	Definition
VE	Vaccine effectiveness

PFIZER CONFIDENTIAL

4. ABSTRACT

Not applicable.

PFIZER CONFIDENTIAL

5. AMENDMENTS AND UPDATES

None.

PFIZER CONFIDENTIAL

6. MILESTONES

Milestone	Planned date
Start of data collection	05 May 2023
End of data collection	12 May 2023
Final study report	12 December 2023

7. RATIONALE AND BACKGROUND

Data suggest severe acute respiratory syndrome coronavirus 2 (SARS-CoV-2) likely follows a seasonality pattern as with other respiratory viral infections such as influenza; where activity peaks during the traditional winter viral respiratory season.¹ CDC guidance for the 2020 and 2021 flu seasons included a recommended time interval of at least 14 days between flu and COVID-19 vaccines.² Based on updated data, the CDC has revised their recommendations that COVID-19 vaccines may be co-administered with seasonal influenza vaccines (SIV).³ Specifically, COVID-19 and SIV can be administered concomitantly, and routine administration of all age-appropriate doses of vaccines simultaneously is recommended for children, adolescents, and adults.³ A systematic literature review of 30 studies revealed that when SIV and COVID-19 booster vaccines are combined, there is potential for an increase in the uptake of the COVID-19 vaccine, predominately because many individuals are accustomed to taking SIV annually.⁴

Studies have reported similar safety and immunogenicity among those who received co-administered COVID-19 vaccine and SIV compared to those who received these vaccines separately.⁵⁻¹¹ Three of these studies were clinical trials comparing safety and immunogenicity between SIV and COVID-19 co-administration versus SIV or COVID-19 alone. In these three clinical trials, no safety concerns or immune interferences were found regardless of the vaccines or the age of vaccinated subjects (18-64 or 65+).^{6,9-11} Hause et al in a retrospective cohort study of self-reported vaccine data found a significant increase in reports of systemic reactions 0-7 days following co-administration of a COVID-19 mRNA booster vaccines with an SIV compared to COVID-19 mRNA vaccine alone;⁵ whereas results from a VAERS database⁸ and the National Health Interview Survey⁷ analyses found no unusual or unexpected patterns of AEs or differences in symptom severity.

Regarding efficacy/effectiveness, one study was identified and reviewed. Novavax's NVX-CoV2373 COVID-19 vaccine efficacy when co-administered with the quadrivalent influenza cell-based vaccine Flucelvax (Seqirus UK, Maidenhead) among individuals aged 18 to <65 years was 87.5% (95% CI -0.2 to 98.4); was slightly attenuated compared to when administered alone (89.8% (95% CI 79.7-95.5).⁹

Although the above studies evaluated safety, immunogenicity and efficacy, the proportion of individuals receiving concomitantly administered COVID-19/influenza vaccines in routine clinical practices is not well characterized and has the potential to be a large percentage of vaccine recipients. Further, it is unknown whether receiving COVID-19/influenza vaccines concomitantly alters subsequent health outcomes. Therefore, the aim of this study is to evaluate within the context of a large national healthcare claims database in the US the proportion of bivalent COVID-19/influenza vaccines concomitantly administered; the characteristics of patients who receive concomitant administration and subsequent health outcomes among groups defined by vaccine administration.

8. RESEARCH QUESTION AND OBJECTIVES

Primary Objective 1: To describe the proportion of Pfizer-BioNTech bivalent mRNA COVID-19/influenza vaccines that are concomitantly administered, and the characteristics of patients who receive concomitant administration.

Primary Objective 2: To estimate vaccine effectiveness (VE) of concomitant administration of a single dose of the mRNA Pfizer-BioNTech bivalent COVID-19 vaccine and a licensed flu vaccine versus either vaccine alone against all-cause hospitalization or acute respiratory illness requiring hospitalization, emergency department/urgent care or outpatient encounters.

9. RESEARCH METHODS

9.1. Study Design

[figure not shown]
This structured secondary data collection study will be a retrospective, cohort design to describe concomitant vaccine uptake and subsequent outcomes during one influenza vaccination season. Individuals will be indexed on the date of their first Pfizer-BioNTech mRNA bivalent COVID-19 or influenza vaccine. Exposure groups will be assigned as follows:

- Group 1: Same day (Pfizer-BioNTech mRNA bivalent COVID and flu on the same day);
- Group 2: COVID alone (Pfizer-BioNTech bivalent COVID only);
- Group 3: flu alone (influenza vaccine of any type only).
- CCI

A one year lookback period prior to the index vaccination will be used to identify covariates. Individuals will be followed starting 15 days after vaccination until experiencing one of the following: 1) outcome 2) disenrollment 3) receipt of a second vaccine of the same type 4) receipt of the other vaccine or any type of COVID-19 vaccine 5) end of data or 6) death. Only Pfizer-BioNTech mRNA bivalent COVID-19 vaccine will be assessed. All types of influenza vaccines recommended for the eligible population will be eligible for inclusion, but for the 65+ age group only enhanced influenza vaccines will be included.

PFIZER CONFIDENTIAL

Figure 1. Overall Study Design

9.2. Setting

The study period will be 31 August 2022 through 14 February 2023, but data will be used going back to 31 August 2021 to ascertain baseline covariates. The study population will include adults who were enrolled in the Optum Clininformatics Database as of 31 August 2022 (the date when the Pfizer-BioNTech bivalent mRNA vaccine was authorized), and have received a Pfizer-BioNTech mRNA bivalent COVID-19 or influenza vaccine during the study period.

9.2.1. Inclusion Criteria

Patients must meet all of the following inclusion criteria to be eligible for inclusion in the study:

1. Enrolled in Optum claims database as of 31 August 2022 (date bivalent authorized).
2. Has a Pfizer-BioNTech mRNA bivalent COVID-19 or influenza vaccine (any type) between 31 August 2022 and 30 January 2023 (earliest vaccine is index date).
3. Aged ≥ 18 years on the index date.
4. 365 days of continuous enrolment prior to index date.

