Prior diabetes	Patient Characteristics	Any code (any setting) within the 1 year baseline for diabetes
Prior kidney disorders	Patient Characteristics	Any code (any setting) within the 1 year baseline for kidney disorders
Month of index date	Patient Characteristics	August/September, October, November, December, January (Note: August will be combined with September as only 1 day of August will be included in the cohort). Model specification: categorical
Prior Influenza vaccination	Patient Characteristics	One claim (NDC or CPT) for influenza vaccine of any type measured between 31 August 2021 – 31 May 2022 Model specification: dichotomous (yes/no)
COVID-19 vaccination in the 1 year prior	Patient Characteristics	One claim (NCD, CPT, procedures) for COVID vaccine of any type in the 365 days before index separated into the following time periods: 
 Recent vaccination: ≤ 60 days prior to index Older vaccination: Between 61 and 365 days prior to index No evidence of vaccination in the prior year If there is evidence of >1 COVID vaccination in the 365 days prior to index, patients are categorized using the date of the most recent dose administered during the baseline period. Model specification: categorical (3 level)
Time from last COVID-19 vaccine dose (Due to the likelihood of misclassification, this variable will be used for descriptive table only, not for model)	Patient Characteristics	Number of days from last COVID-19 vaccine dose. Reported as categories: ^{17,18} <60 days, 60-179, ≥ 180 , not applicable. Continuous statistics including mean, standard deviation (SD), median (Q1-Q3), minimum, and maximum, among those with a prior dose.
Monovalent mRNA COVID-19 vaccine in the 60 days prior to index (Note for descriptive table only, not for model due to collinearity with covid vaccine in the prior year above)	Patient Characteristics	Yes/No. One claim (NCD, CPT, procedures) for monovalent mRNA COVID-19 vaccine between 01 July 2022 – 30 August 2022

PFIZER CONFIDENTIAL

Table 4. Covariates

Variable	Role	Operational definition

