9.7. Data Analysis

There is not a separate Statistical Analysis Plan document for this study. All methodology for summary and statistical analyses of data collected in this study is contained in this section. All computations and generation of tables will be performed using Statistical Analysis System (SAS) version 9.4 or higher (SAS Institute, Cary, NC, US).

All analyses will be conducted for the following age subgroups: 18-64 and 65+.

Descriptive statistics will be presented to describe baseline characteristics by vaccination exposure group. Baseline characteristics will be described by frequency distribution for categorical variables while continuous variables expressed in terms of their mean and standard deviation or median and interquartile range (IQR) as appropriate. In general, missing or unavailable data will not be imputed and data will be analyzed as they are recorded in the database.

To account for imbalance in patient characteristics between the vaccine exposure groups, 2 separate logistic regression models will be used to create a propensity score used to calculate an inverse probability of treatment weights (IPTW). The two models will be as follows: Same day vs COVID-19 alone, and separately Same day vs Flu alone. Weights will be stabilized to avoid exertion of outliers, and we will further evaluate whether there is a need to truncate at the 1st and 99th percentile. Covariate balance before and after weighting will be assessed using standardized mean differences, separately for the same day/COVID-19 alone and Same day/flu alone comparisons. All variables listed in “[Covariates](#)” section with model specification instructions will be included in the score. If there are model convergence issues, changes in model specification may occur (eg, dropping variables with very low prevalence, categories may be collapsed further etc). Variables with residual imbalance will be included in the model for further adjustment.

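### The fixed 2021-22 window for prior influenza vaccination reaches back further than the 365-day enrolment rule guarantees, so unobserved doses in some newer members are coded as no

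*Combined protocol and SAP*

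**What the plan says.** Section 9.2.1 sets two enrolment conditions. Criterion 4 requires "365 days of continuous enrolment prior to index date". Criterion 1 requires membership on a single day, 31 August 2022. Index dates run from 31 August 2022 to 30 January 2023.

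Table 4 in Section 9.3.4 defines prior influenza vaccination as "One claim (NDC or CPT) for influenza vaccine of any type measured between 31 August 2021 – 31 May 2022", with a dichotomous model specification. Because it carries a model specification, Section 9.7 puts it in both propensity scores.

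Three other statements bear on the point:

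- Section 9.1: "A one year lookback period prior to the index vaccination will be used to identify covariates".
- Section 9.2: "data will be used going back to 31 August 2021 to ascertain baseline covariates". This says which data are drawn. It does not require a member to have been enrolled on that date.
- Section 9.7: in general, "missing or unavailable data will not be imputed", and data are analysed as recorded.

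**The concern.** With yes/no coding, the absence of a claim means no, whether the member was observed and unvaccinated or was not yet enrolled. Two people with the same index date and the same vaccination history can therefore be coded differently only because one joined the plan later.

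This covariate is the plan's most direct marker of the habit of taking influenza vaccine. Same day and COVID alone differ precisely in whether an influenza vaccine was given at index, so it should predict membership of those groups strongly. To the extent it is misrecorded, weighting leaves some confounding behind. The standardized mean differences cannot show this, because they are computed on the recorded value. The Objective 1 description of prior vaccination would also be somewhat too low in the affected members.

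**Working it through.** **The plan's own figure.** The earliest index date, 31 August 2022, minus 365 days is 31 August 2021. This reproduces the data start in Section 9.2.

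**Inputs.** The covariate window is 31 August 2021 to 31 May 2022: 1 + 30 + 31 + 30 + 31 + 31 + 28 + 31 + 30 + 31 = 274 days. There are 153 possible index dates.

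**Formula.** For index date d, enrolment is guaranteed only from d − 365. Maximum unobserved days = (d − 365) − 31 August 2021. Share = unobserved days / 274.

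| Index date | Enrolment guaranteed from | Maximum unobserved days | Share of window |
|---|---|---|---|
| 31 Aug 2022 | 31 Aug 2021 | 0 | 0% |
| 1 Oct 2022 | 1 Oct 2021 | 31 | 11.3% |
| 1 Nov 2022 | 1 Nov 2021 | 62 | 22.6% |
| 1 Dec 2022 | 1 Dec 2021 | 92 | 33.6% |
| 1 Jan 2023 | 1 Jan 2022 | 123 | 44.9% |
| 30 Jan 2023 | 30 Jan 2022 | 152 | 55.5% |

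Only the first of the 153 index dates guarantees the whole window. The missing stretch is always the start of the season. For example, a member who joined on 1 November 2021 and is indexed on 1 November 2022 is eligible, yet has no claims for September and October 2021.

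**Does another rule close the gap?** No. For any index date after 31 August 2022, criterion 4 already implies criterion 1, so criterion 1 adds no earlier history. The other modelled covariates with a lookback use 180 days, 365 days or one year before index, which criterion 4 covers. The other fixed-date covariate (monovalent vaccine, July to August 2022) is descriptive only and is also covered. The gap is specific to this variable.

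**Illustration of size (all inputs assumed except the 63%).** Suppose 1% to 4% of the cohort joined after 31 August 2021 and 40% to 70% of their prior-season doses are missed. If prior vaccination is as common in them as in others, the share of true yes values lost overall is 0.01 × 0.40 = 0.4% to 0.04 × 0.70 = 2.8%, so sensitivity s is 0.996 to 0.972.

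Let p1 and p2 be the true proportions previously vaccinated in Same day and COVID alone, with 63% in Same day (Section 9.5), P = 0.63·p1 + 0.37·p2, and RR the covariate's association with the outcome. Assume the same s in both groups and no false yes values. After weighting on the recorded value:

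- share truly vaccinated among recorded no: q = p(1 − s)/(1 − p·s)
- mean relative risk in a group: R = s·P·RR + (1 − s·P)·[1 + (RR − 1)·q]

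With p1 = 0.80, p2 = 0.40, RR = 1.5 and s = 0.972: P = 0.652, s·P = 0.634, q1 = 0.0224/0.2224 = 0.101, q2 = 0.0112/0.6112 = 0.018, R1 = 1.335, R2 = 1.320, and R1/R2 = 1.011. With s = 0.996 the ratio is 1.002. More extreme inputs (p1 = 0.90, p2 = 0.40, RR = 2) give 1.005 to 1.033.

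**The case against.** The case against giving this much weight is good, and most of it stands.

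- **The gaps are upper limits.** They describe the latest possible joiner at each index date. Longer-enrolled members are fully observed, and a newer member with a claim in the observed part is still coded yes. A member who joined on 1 January 2022 is eligible only if indexed in January 2023.
- **Other terms carry related information.** Month of index is in the propensity score, as are prior COVID-19, Shingrix and pneumococcal vaccination, wellness visits, outpatient visits and testing. Month of index cannot separate newer from longer-enrolled members within a month, so the mitigation is partial.
- **Negative control outcomes** (urinary tract infection, accidental injury, hospitalization in days 1 to 14) could signal residual confounding of this kind. They would not identify or correct this cause.
- **The strong-predictor argument is specific to one comparison.** In Same day versus Flu alone, everyone received an influenza vaccine at index.
- **Section 9.9 already concedes missing vaccine claims.** It does so for doses with no claim filed, not for doses given before enrolment.

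A reader might infer that 40% to 70% of previously vaccinated newer members are miscoded. The documents give no distribution of doses or joining dates, and that range does not suit early index dates: for 1 October 2022 at most 31 of the 274 days are in question. The mismatch itself is not answered by any of this.

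**Conclusion.** The mismatch is established from the text by date arithmetic alone. Followed as written, the plan codes some unobservable doses as no in a covariate used in both propensity scores, with a maximum gap of 31 days (index 1 October 2022) to 152 days (index 30 January 2023) out of 274.

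The consequence is a risk of misclassification, not a measured bias. A reader might infer that the hazard ratios are materially distorted or that the weighting fails. The documents do not support that: they give neither the number of members who joined after 31 August 2021 nor any difference in that number between groups. Under the assumed inputs above, the ratio moves by about 0.2% to 1.1%, or 0.5% to 3.3% in the more extreme case, treating this covariate as the only adjustment. The planning margin is 1.15. A larger effect would need newer members to be unevenly spread between the groups. The point matters mainly for Same day versus COVID alone and is worth correcting because the correction is cheap.

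**What to change.** Choose one of two changes.

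1. **Change enrolment.** Replace criteria 1 and 4 with continuous enrolment from 31 August 2021 through the index date. This gives 365 days of history for an index on 31 August 2022 and 365 + 152 = 517 days for 30 January 2023, with no unobserved days. The cost is the loss of members who joined between September 2021 and January 2022. Their number cannot be computed from the documents.
2. **Change the covariate.** Keep the 365-day rule and code three levels in both propensity models: yes; no, with the full window observed; no claim, with the window not fully observed. Add a sensitivity analysis restricted to members enrolled since 31 August 2021. No patients are lost. The cost is one derived variable and one extra run.

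With either change, reconcile Section 9.1 with Table 4. The one-year lookback and the fixed window disagree for every index date after 31 August 2022, and the fixed window starts 517 days before the latest index. Cutting the variable to one year before index would not solve the problem: early-season doses would then be lost for all later-indexed patients, not only newer members. Neither change needs data from before the date already named in Section 9.2.

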9.2.2. Exclusion Criteria

Patients meeting any of the following criteria will not be included in the study:

1. Patients with a second dose of any type of bivalent mRNA COVID-19 or flu vaccine, disenrolled or died within 14 days following the first dose.
2. Has prior COVID-19 diagnosis (U07.1, any setting, any position) within 90 days (per CDC guidance¹² on length of time before receiving a vaccine) before and on index.
3. Has influenza vaccine between 01 August -30 August 2022 (before study period).

PFIZER CONFIDENTIAL

4. Has a COVID-19 or influenza diagnosis code in any setting within 14 days after index vaccination (excluded from all cohorts).
5. For patients 65+, had a standard dose influenza vaccine or unknown type influenza vaccine.
6. Has Moderna mRNA bivalent COVID-19 vaccine or monovalent vaccine of any type on index date.

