9.3. Variables

9.3.1. Exposure

Table 1. Vaccination Status Variables		
Variable	Role	Operational definition
Group 1: Same Day (Concomitantly administered Pfizer-BioNTech COVID-19 mRNA bivalent vaccine + influenza vaccine)	Exposure	
Patients meeting the following criteria will be included in the Same Day cohort:
 
1. NDC or CPT codes for both the Pfizer-BioNTech mRNA bivalent COVID-19 vaccine and an influenza vaccine during the study period.2. The first Pfizer-BioNTech mRNA bivalent COVID-19 vaccine and influenza vaccine NDC or CPT codes during the study period occurred on the same date.3. No influenza vaccine NDC or CPT code between 01 August 2022 and 30 August 2022. 
If the patient receives >1 mRNA bivalent COVID-19 vaccine or influenza vaccine during follow-up, the patient is censored on the date of the NDC or CPT code for the second vaccine of the same type. mRNA bivalent COVID-19 and influenza vaccine NDC and CPT codes are listed in Appendix Table 1.

Group 2: COVID alone (COVID-19 mRNA bivalent vaccine alone)	Exposure	
Patients meeting the following criteria will be included in the COVID-19 alone cohort:
 
1. Pfizer-BioNTech mRNA bivalent COVID-19 vaccine NDC or CPT code during the study period and no influenza vaccine on that date.2. No influenza vaccine NDC or CPT code between 01 August 2022 and 30 August 2022. 
If the patient receives >1 mRNA bivalent COVID-19 vaccine (any type) during follow-up or an influenza vaccine, the patient is censored on the date of the NDC or CPT code for the second mRNA bivalent COVID-19

PFIZER CONFIDENTIAL

Table 1. Vaccination Status Variables

Variable	Role	Operational definition
		vaccine/influenza vaccine. mRNA bivalent COVID-19 vaccine NDC and CPT codes are listed in Appendix Table 1 .

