9.5. Study Size

The sample size for this study is fixed by the duration of the observation window. All subjects who meet the inclusion/exclusion criteria will be included in the analyses.

Feasibility analyses from 31 August 2022- 16 January 2023 confirmed the availability of data to identify vaccinated subjects. Table 5 below shows the estimated number of patients in each group.

Table 5. Estimated Number of Patients in Each Vaccination Exposure Group

	Group 1: Same Day	Group 2: COVID- 19 alone	Group 3: Flu alone	CCl [REDACTED]
18-64	244,864	144,695	772,418	CCl [REDACTED]
65+	382,806	225,842	1,351,093	CCl [REDACTED]

Composite COVID-19 hospitalizations/UC/ED

For 65+, and the Group 1 vs Group 2 comparison of the COVID-19 related composite hospitalizations/ED/UC endpoint, we assume the percentage of patients in Group 1 will be 63% and the expected percentage of patients in Group 1 and Group 2 with an event overall will be 0.56%. If we use a non-inferiority margin of 1.15 for the upper bound of the 95% CI, 1-sided alpha of 0.025, and 80% power, and an expected HR of 1, then we would need 1,724 events resulting in 193,548 patients in Group 1, and 113,671 in Group 2, which meets our current estimated sample size.¹⁹

For 18-64, and the Group 1 vs Group 2 comparison of the COVID-related composite hospitalizations/ED/UC endpoint, we assume the percentage of patients in Group 1 will be 63% and the expected percentage of patients in Group 1 and Group 2 with an event overall will be 0.066%. If we use a non-inferiority margin of 1.15 for the upper bound of the 95% CI, 1-sided alpha of 0.025, and 80% power, and an expected HR of 1, then we would need 1,638,003 in Group 1, and 962,002 in Group 2, which does not meet our current estimated sample size.

Composite influenza hospitalizations/UC/ED

For 65+ and for the Group 1 vs Group 3 comparison of the flu-related composite hospitalizations/UC/ED endpoint, we assume the percentage of patients in Group 1 will be 23% and the expected percentage of patients in Group 1 and Group 3 with the endpoint overall will be 0.3%. If we use a non-inferiority margin of 1.15 for the upper bound of the 95% CI, 1-sided alpha of 0.025, and 80% power, and an expected HR of 1, then we would need 2,269 events resulting in 176,179 in Group 1, and 589,817 in Group 3, which meets our current estimated sample size.

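### The single exclusion list, built for the VE comparison, also governs Primary Objective 1, so the 65+ uptake result covers co-administration with enhanced influenza vaccine only

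*Combined protocol and SAP*

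**What the plan says.** Section 8 sets the first primary objective: "To describe the proportion of Pfizer-BioNTech bivalent mRNA COVID-19/influenza vaccines that are concomitantly administered", together with the characteristics of those patients. Section 7 gives the reason, which is that co-administration in routine practice is poorly characterised.

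Section 9.2 draws the population from people who "have received a Pfizer-BioNTech mRNA bivalent COVID-19 or influenza vaccine during the study period". Inclusion criterion 2 in section 9.2.1 is equally broad: "Has a Pfizer-BioNTech mRNA bivalent COVID-19 or influenza vaccine (any type) between 31 August 2022 and 30 January 2023".

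Section 9.2.2 opens with "Patients meeting any of the following criteria will not be included in the study", and its fifth item reads "For patients 65+, had a standard dose influenza vaccine or unknown type influenza vaccine". Section 9.1 states the same restriction: "for the 65+ age group only enhanced influenza vaccines will be included". Section 9.5 adds: "All subjects who meet the inclusion/exclusion criteria will be included in the analyses".

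In Table 1 (section 9.3.1) the COVID-alone group needs a "Pfizer-BioNTech mRNA bivalent COVID-19 vaccine NDC or CPT code during the study period and no influenza vaccine on that date". A COVID-alone patient who is later vaccinated against influenza is kept and censored at that date. Table 4 records the type of influenza vaccine given at index (enhanced, standard or unknown).

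The visible part of section 9.7 plans baseline characteristics by exposure group and the outcome models. It sets no separate population for uptake. The limitations in section 9.9 do not mention the enhanced-only restriction.

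**The concern.** Restricting patients aged 65+ to enhanced influenza vaccine makes the VE groups more alike. A description of uptake has a different aim. A 65-year-old given the bivalent vaccine and a standard-dose influenza vaccine on the same day is a concomitant recipient in routine practice, yet appears nowhere in the Objective 1 result. The 18-64 stratum keeps every influenza vaccine type, so the two age-specific uptake figures would not describe the same thing.

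Exclusions 1 and 4 raise a similar problem. They remove people who, within 14 days, have a second dose, disenrol, die, or receive a COVID-19 or influenza diagnosis. That fits follow-up starting on day 15. It does not fit a count of who was co-vaccinated on day 0.

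At stake is the meaning of one of two primary results. A reader would take the 65+ figure as routine co-administration when it is narrower than that.

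**Working it through.** **Scope, from the text.** Section 9.2.2 applies its list to the study as a whole. Section 9.5 applies the inclusion and exclusion criteria to the analyses without distinguishing objectives. No visible sentence exempts Objective 1. Exclusion 5 and section 9.1 together leave only enhanced-vaccine recipients in the 65+ Same Day group.

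**Inputs.** Table 5 feasibility counts for 65+: Same Day A = 382,806; COVID alone B = 225,842; Flu alone C = 1,351,093. The documents do not say whether these were counted before or after exclusion 5.

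**The plan's own figure.** Section 9.5 assumes that 63% of Groups 1 and 2 are in Group 1. From Table 5, A/(A+B) = 382,806/608,648 = 62.9%, so it reproduces.

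**Direction of exclusion 5 for Same Day plus COVID alone, read at the index date.** Let s1 be the fraction of Same Day patients dropped. COVID-alone patients have no influenza vaccine on the index date, so none of them is dropped. The share becomes (1−s1)A / [(1−s1)A + B], which is below A/(A+B) for every s1 > 0.

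**Illustration only.** The values of s1 below are assumptions; the documents give none.

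| Assumed s1 | Table 5 counted before exclusion 5: share after removal | Table 5 counted after exclusion 5: share once restored |
|---|---|---|
| 0% | 62.9% | 62.9% |
| 5% | 61.7% | 64.1% |
| 10% | 60.4% | 65.3% |
| 20% | 57.6% | 67.9% |
| 30% | 54.3% | 70.8% |

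Example at 10%: removal gives 344,525/(344,525 + 225,842) = 60.4%. Restoration gives 382,806/0.9 = 425,340, and 425,340/(425,340 + 225,842) = 65.3%.

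**Direction for other denominators.** Let s3 be the fraction dropped from Flu alone. Let F be the number of flu-first patients who later receive the bivalent vaccine, and sF the fraction of them dropped.

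- Influenza recipients (A+C): the share falls only if s1 > s3.
- All three visible groups: it falls only if s1 > s3 × C/(B+C). If Table 5 precedes exclusion 5, C/(B+C) = 1,351,093/1,576,935 = 0.857.
- Bivalent recipients including flu-first patients: it falls only if s1 > sF × F/(B+F).

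None of s1, s3, sF or F is in the documents, so none of these directions can be settled.

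**Time anchor.** Exclusions 2, 3, 4 and 6 each state a window or date; exclusion 5 states none. Read literally, it could remove a 65+ COVID-alone patient because of a standard-dose vaccine given after index, whom Table 1 would keep and censor. If a fraction s2 of COVID-alone patients were dropped in this way, the share would be (1−s1)A / [(1−s1)A + (1−s2)B], which falls only if s1 > s2. The direction above therefore depends on the index-date reading.

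**The case against.** The strongest reply is that the restriction is deliberate, is stated in both section 9.1 and section 9.2.2, and would show in age-specific tables of index vaccine type. That is right, and the point does not treat it as a mistake or as hidden. It remains that a rule suited to VE is applied to a descriptive objective whose stated purpose is routine practice, with no label on the result.

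A second reply is that no effect on the proportion has been sized. That also stands. What is shown is a narrower scope, plus a direction for one denominator under one reading.

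A reader might go further in three ways that the documents do not support:

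- **That Objective 1 has no denominator at all, and that this causes the restriction.** A group entry is redacted in section 9.1, Table 1 and Table 5, and so is a block of section 9.7, so a definition may exist there. Any denominator would in any case leave exclusion 5 in force. Naming the denominator is a supporting wording point only.
- **That the spread across denominators measures the harm.** The 65+ same-day share is 62.9% of Groups 1+2, 22.1% of Groups 1+3 (382,806/1,733,899) and 19.5% of the three visible groups (382,806/1,959,741). That spread comes from the choice of base and says nothing about exclusion 5.
- **That the exclusions together understate uptake.** Exclusion 3 removes people vaccinated against influenza in August 2022, which can raise the same-day share among bivalent recipients. No net direction follows.

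**Conclusion.** The point holds as a matter of scope. As written, the 65+ uptake result and recipient characteristics describe co-administration with enhanced influenza vaccine only, and both age strata condition on events in the 14 days after vaccination. For Same Day plus COVID-alone patients aged 65+, exclusion 5 lowers the same-day share for any nonzero dropped fraction, provided it is read at the index date. The size is unknown, and the table of assumed fractions is not an estimate. For other denominators the direction is open. The conclusion rests on the visible text; redacted passages could hold a separate Objective 1 population, but the visible parts of sections 9.2.2 and 9.5 make no room for one. VE is affected only through the missing time anchor in exclusion 5. This should be changed, since the remedy is cheap and concerns a primary objective.

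**What to change.** - For Objective 1, report the same-day proportion and recipient characteristics by age group before exclusions 5, 1 and 4. Split 65+ by enhanced, standard and unknown influenza vaccine, and name the denominator of each proportion.
- Keep these exclusions for the Objective 2 cohort.
- Word exclusion 5 so that it refers to the influenza vaccine given on the index date, in line with Table 4 and the Table 1 censoring rule.
- Label the uptake and VE populations separately.
- If the restriction is kept for Objective 1, label the 65+ result as co-administration with enhanced influenza vaccine only and say so in section 9.9.

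The cost is protocol wording and one extra descriptive table from data already held, double programmed as section 9.8 requires. The uptake and VE populations will then differ in size, and the report must explain why.
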